## 5. TREATMENT OF SUBJECTS

## 5.1 Investigational treatment

## Mindfulness Based Cognitive Therapy (MBCT) + TAU

This intervention will consist of usual care, with MBCT in adjunct. MBCT is a manualised group skillstraining program (Segal, Williams, & Teasdale, 2012) designed as a relapse prevention programme for patients with recurrent depression. The training consists of eight weekly sessions of 2.5 hours, plus one day of silent practice. In addition, participants are instructed to practice 45 minutes a day. The program includes both formal and informal meditation exercises. Cognitive techniques that are part of the program include psychoeducation, monitoring and scheduling of activities, identification of negative automatic thoughts and devising a relapse prevention plan. The MBCT intervention offered in the current study will be based on the 8-week MBCT course developed by Segal et al. (2012), but will be adapted to address the needs of BD patients. A few examples of these adaptations are as follows: psychoeducation about manic symptoms in addition to psychoeduction about depression; introducing the 3-minute breathing space earlier in the programme and more often during sessions, especially when strong emotions are present; repeatedly bringing the focus to self-care; and making use of the mindful movement (yoga) exercises more frequently. All group sessions will be conducted at the respective mental health sites, with each group comprising 8 - 12 participants.

## Mindfulness teachers

The mindfulness training will be taught by teachers qualifying the advanced criteria of the Association of Mindfulness Based Teachers in the Netherlands and Flanders, which include a) a minimum of 150 hours of education in MBSR/MBCT background and theory, training in teaching formal and informal meditation practices, psycho-education and inquiry, supervision and giving an MBSR or MBCT course including a reflection report; b) relevant professional training; c) minimum of three years of practicing meditation regularly and attending retreats; d) having attended MBSR / MBCT as a participant; e) continued training; and f) giving a minimum of two courses per two year. All teachers will receive additional training in the study protocol at the start of the project. We will organize peer supervision meetings every month during the intervention phase of the trial. Teacher competency will be assessed by the Mindfulness-based Interventions - Teacher Assessment Criteria (MBI: TAC, Crane et al., 2012). Videotapes of a random selection of sessions will be assessed by assessors who are familiar with this mindfulness-based program, are 'proficient' mindfulness teachers (level 5) and have received training in the use of these assessment criteria. An early study of the psychometric properties of the MBI:TAC suggests it has good reliability, face validity and promising evidence of validity (Crane et al., 2013).

## Comparator: Treatment as usual (TAU)

Usual care of BD patients typically consists of pharmacotherapy, psycho-education and selfmanagement interventions (usually with a psychiatric nurse). According to the guidelines (Trimbos Instituut, 2015), these interventions will be or will have been offered to patients prior to participation in the current study. It is expected that a large majority of participants receive some form of pharmacotherapy. Because of the clinical representativeness, we will not restrict TAU in any way. So switching, tapering or augmenting of medication might be part of TAU. We will keep a careful record of this in order to examine and control for possible differences between the two groups. However, frequent psychological treatments, i.e. fortnightly or more, such as (group-based) CBT, will be an exclusion criterion for the current RCT because of practical and methodological reasons. For a detailed description of the biological treatment options that are part of TAU, such as several pharmacotherapeutic options, electroconvulsive therapy, and heliotherapy, we refer to the clinical guidelines "Multidisciplinaire Richtlijn Bipolaire Stoornissen (derde, herziene versie)", pp 121-167 (Trimbos Instituut, 2015). Detailed information for each individual pharmacotherapeutic option can be found on the pharmacotherapeutic compass: https://www.farmacotherapeutischkompas.nl/ (Zorginstituut Nederland, 2017).

#### 6. METHODS

#### 6.1 Study parameters/endpoints

Outcome measures will be administered at 6 points in time: baseline (T0) and 3, 6, 9, 12 and 15-month follow-up (T1 – T5).

#### 6.1.1 Main study parameter/endpoint

The primary endpoint of the study is severity of depressive symptoms at 3 months follow-up (T1), assessed with the *Inventory of Depressive Symptomatology – Clinician administered* (IDS-C; Akkerhuis, 1997). The IDS-C has good psychometric qualities (Rush, Gullion, Basco, Jarrett, & Trivedi, 1996; Trivedi et al., 2004) and will be administered by trained research assistants.

#### 6.1.2 Secondary study parameters/endpoints

#### Clinician-administered measures

- Structured Clinical Interview for DSM-IV-TR Axis I Disorders (SCID-I; First, Spitzer, Gibbon, & Williams, 1996) or its successor for DSM 5 when available, to assess depressive and manic relapses. The SCID-I will be used to retrospectively assess possible relapses/recurrences in the past 3 months at each time point. The Dutch version of the SCID-I shows good to excellent inter-rater reliability (Lobbestael, Leurgans, & Arntz, 2011).
- Young Mania Rating Scale (YMRS; Young, Biggs, Ziegler, & Meyer, 1978), Dutch translation. The YMRS is an 11-item clinician-administered rating scale to assess the severity of (hypo)manic symptoms. It was found to be a reliable, valid, and sensitive rating scale to measure the severity of mania (Young et al., 1978).
- Functioning Assessment Short Test (FAST; Rosa et al., 2007), Dutch translation. The FAST is
  a brief instrument designed to assess the main functioning problems experienced by
  psychiatric patients, particularly bipolar patients. It comprises 24 items that assess impairment
  or disability in six specific areas of functioning: autonomy, occupational functioning, cognitive
  functioning, financial issues, interpersonal relationships, and leisure time. It has been shown
  to have strong psychometrics properties in terms of high internal consistency, test-retest
  reliability, and concurrent validity, and its ability to detect differences between euthymic and
  acute BD patients (Rosa et al., 2007).

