## 2. OBJECTIVES

Primary Objective:

• Is MBCT as an adjunctive treatment to TAU more effective in reducing depressive symptoms in patients with bipolar disorder, compared to TAU alone?

Secondary Objective(s):

- Is MBCT more effective than TAU in reducing levels of (hypo)manic and anxiety symptoms, the risk of relapse in depression or (hypo)mania, and ruminative brooding?
- Is MBCT equally effective in patients with < 12 mood episodes compared to patients with =/> 12 episodes?
- Is MBCT more effective than TAU in improving mindfulness, self-compassion, functioning, and mental health/well-being?
- From the viewpoint of the society, is adding MBCT to TAU preferable in terms of societal costs and QALYs, compared to TAU alone?

Our hypothesis is that participants allocated to MBCT will have fewer depressive, (hypo)manic, and anxiety symptoms and experience fewer (hypo)manic or depressive episodes than those allocated to TAU over the 15 months study period. In addition, we hypothesize that MBCT will be associated with improvement in several areas of functioning and well-being. Furthermore, we expect that positive outcomes will be (partially) mediated by a reduction of ruminative thinking, and improvement of mindfulness and self-compassion skills.

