## 4.4 Sample size calculation

Sample size calculation is based on the estimated change in depressive symptoms form pre- to posttreatment. As we aim to include patients with all levels of depressive symptoms, we based our calculation on a previous study conducted at the Radboudumc Centre for Mindfulness (van Aalderen et al., 2012). In this study, levels of depression as assessed with the Inventory of depressive symptomatology – self-rated (IDS-SR) decreased in the MBCT+TAU group (n = 102) from 14.9 ( $\pm$  9.2) to 10.3 ( $\pm$  7.8) whereas the TAU group (n = 103) showed no change in depression levels (pretreatment: M = 16.2 ( $\pm$  9.4) and posttreatment: M = 16.2 ( $\pm$  9.8). This corresponded to an effect size of 0.5 for reduction of depressive symptoms in patients with recurrent (unipolar) depression (remitted n = 124, currently depressed n = 58). Based on a two-sided test with an alpha of 0.05 and a power of 80%, with an estimated effect size of 0.5, including a design factor of 1 – r2 (0.75), and taking account of a conservative estimate of 40% loss to follow-up, we intend to recruit N = 160 patients (80 per group).

We anticipate that about 25% of the population will have to be excluded due to (hypo)manic symptoms (when exceeding the maximum on the Young Mania Rating Scale) or other exclusion criteria. We further expect about 25% of the eligible patients to be interested in the study.

Approximately 690 BD patients are treated in ProPersona, with 518 (75%) meeting the inclusion criteria, of whom 130 (25%) would probably be interested to participate. The intended number of participants (n = 60) falls comfortably within this estimate. The number of BD patients treated in Dimence is about 900, with 675 (75%) meeting the inclusion criteria, of whom 169 (25%) would probably be interested to participate. Again, the intended number of participants (n = 50) falls well within this estimate. Approximately 650 BD patient are treated in Altrecht, with 100-150 new patients per year. About 487 (75%) of BD patients would be meeting the inclusion criteria, of whom 122 (25%) would probably be interested. The intended number of participants (n = 50) therefore seems feasible. Moreover, we will recruit patients through the patient association Vereniging voor Manisch Depressieven en Betrokkenen (VMDB) and the psychiatry department of the Canisius Wilhelmina

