## 6.3 Study procedures

Figure 2 provides a flowchart of the study procedures from referral to the final assessment. Patients will be recruited from several specialized, outpatient clinics in the Netherlands; ProPersona, Dimence, and Altrecht, and through the patient association; Vereniging voor Manisch Depressieven en Betrokkenen (VMDB). They will receive a letter from their attending clinicans, informing them about the study with an included information leaflet. This way, patients are free to choose whether to participate in the study, without feeling obligated to their clinicans when asked face-to-face. Interested patients are, after verbal consent is obtained, invited for a screening by telephone to assess global eligibility. Eligible patients will receive more information and a detailed description of the study procedure. After one week, patients will be contacted by telephone to assess whether they are still interested in participation. Patients who are still interested to participate will be invited for intake with a research assistant, where informed consent is obtained. They are thoroughly screened for in- and exclusion criteria with use of the SCID-I and YMRS. Altogether, this will take about 1.5 hours. When patients are still eligible and interested, they are invited for baseline assessment (T0), which consists of several clinician administered measures (IDS-C and FAST), which will take about 20 minutes. After a short pause, participants are asked to conduct five short computer tasks (Stroop, Emotional Stroop Task, Breathing Focus Task, Self Referent Encoding Task, and Attentional Control Scale). This will take about onee hour. However, it is possible for participants to do only the first part of these measures, so they can skip the computer tasks if necessary. Furthermore, participants are asked to fill in several self-report questionnaires at home (STAI, brooding subcale of RRS, CHIME, SCS-SF, MHC-SF, RPA, CTQ, TiC-P, and EQ-5D-5L). After baseline assessment, patients are randomised to one of two groups: TAU or MBCT + TAU. Participants in the intervention group (MBCT + TAU) will receive an eight-week MBCT training, during which they daily have to document mood fluctuations, changes in medication, and major life events in the Life Chart. Furthermore, participants are asked to document adherence and adverse events in a personal diary. Participants in the comparator group (TAU) will receive their treatment as usual, while they daily document in the Life Chart as well. After three months (T1), participants are invited for follow-up assessment, during which the clinician administered questionnaires (YMRS, IDS-C, FAST, SCID-I) and computer tasks will be conducted again. Furthermore, patients are asked to fill out the online self-report questionnaires a second time. More follow-up assessments will take place after 6 months (T2), 9 months (T3), 12 months (T4), and 15 months (T5). During T2, T3, and T4 assessments patients are approached by telephone to assess depressive, manic, and anxiety symptoms, and global functioning over the past three months (IDS-C, YMRS, FAST, and SCID-I to assess manic and depressive symptoms retrospectively). Furthermore, during these assessments patients are asked to fill out the online questionnaires as well. The assessment at 15 months follow-up (T5), will consist of the clinician adminstered meassurements (IDS-C, YMRS, FAST) and the online self-report measurements (STAI, brooding subcale of RRS, CHIME, SCS-SF, MHC-SF, RPA, TiC-P, EQ-5D-5L). Table 1 provides an overview of the assessments. After 15 months of follow-up the study will end, after which participants in the comparator group will be given the opportunity to participate in a MBCT-course as well.

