- Relapse into a (hypo)manic or depressive episode, which is an expected event in this specific population, since 60% of BD patients relapse within two years (Miklowitz et al., 2009; Oud et al., 2016). The study of Perich et al. (2013), who conducted a RCT of MBCT for BD, found that 59% of participants in the MBCT condition and 48% in the TAU condition reported a (hypo)manic episode, while 59% in the MBCT condition and 68% in TAU reported a depressive episode over a 12 month follow-up period. In that study, the median time to

(hypo)mania relapse was 130 days for MBCT and 143 for TAU. Median time to depressive relapse was 53 days for MBCT and 46 days for TAU.

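### The SCID-I look-back is fixed at 3 months with visits 3 months apart, so a skipped interview leaves a quarter that the SCID-I never covers, even when the patient is interviewed at the next visit

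*Protocol*

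**What the plan says.** Section 2 lists "the risk of relapse in depression or (hypo)mania" among the secondary objectives and hypothesises fewer episodes across the 15 months. Section 6.1.2 names the SCID-I as the instrument for depressive and manic relapses and sets its window: it is to "retrospectively assess possible relapses/recurrences in the past 3 months at each time point". Section 6.1 places the assessments at "baseline (T0) and 3, 6, 9, 12 and 15-month follow-up".

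Section 6.3 describes T1 as an assessment to which patients are invited, with interviews and computer tasks. Of the later contacts it says "During T2, T3, and T4 assessments patients are approached by telephone", again with a three-month look-back.

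No section extends the look-back to the last completed interview. Section 6.6 has dropouts telephoned for the outstanding questionnaires and does not mention a catch-up SCID-I.

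Section 6.1.2 also includes a prospective self-reported Life Chart over the whole study, and section 6.3 has both arms keep it daily. Its stated purpose is finer detail on symptom severity over time. No section uses it to define a relapse or to fill in a missed SCID-I.

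**The concern.** Five windows of 3 months cover 15 months only if every interview takes place and takes place on time. A patient who misses T1 and is reached at T2 is asked about months 3 to 6. Months 0 to 3 are never asked about on the SCID-I, although the patient is there to be asked.

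A first relapse in that quarter can then go unseen, or a later episode can be dated as the first. When visits shift, a stretch of time may be skipped, or one episode may be reported in two windows. This is a rule for collecting data, so an analysis plan can model or impute the missing quarter but cannot recover it.

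**Working it through.** **Plan's own figure.** The only related total is the sample size, which rests on depressive symptoms and not on relapse. It reproduces: 2 x (1.960 + 0.842)^2 / 0.5^2 = 62.8, so 63 per arm; 63 x 0.75 = 47.25, rounded up to 48; 48 / (1 - 0.40) = 80 per arm, 160 in total. Nothing below changes it.

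**Coverage under the stated rule.**

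| Pattern | Months covered by SCID-I | Result |
|---|---|---|
| All visits on time | 0-3, 3-6, 6-9, 9-12, 12-15 | complete, no slack |
| T1 missed, T2 held | 3-6 onward | months 0-3 uncovered |
| T2 held at month 6.5 | 0-3, 3.5-6.5, 6-9, ... | gap 3-3.5, overlap 6-6.5 |

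If the look-back ran from the last completed SCID-I, each pattern would have no gap and no overlap.

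**Where first relapses fall.** The inputs come from the earlier randomised trial of MBCT in bipolar disorder cited in section 7.2.2. For depression: "Median time to depressive relapse was 53 days for MBCT and 46 days for TAU", and "59% in the MBCT condition and 68% in TAU reported a depressive episode over a 12 month follow-up period". For (hypo)mania the medians are 130 days (MBCT) and 143 days (TAU), with 12-month rates of 59% and 48%.

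The medians are read as among relapsers. A crude median over all patients would be impossible for (hypo)mania under TAU, because 0.50 / 0.48 = 1.04 exceeds 1.

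- *Without a model:* both depressive medians lie before day 91, so at least 50% of first depressive relapses fall in months 0-3. As a share of all patients that is 0.50 x 0.59 = 29.5% (MBCT) and 0.50 x 0.68 = 34% (TAU).
- *Assuming exponential times truncated at 365 days:* share in the first quarter = (1 - exp(-91k)) / (1 - exp(-365k)), with k set so that the median matches. This gives 0.697 (MBCT) and 0.747 (TAU) for depression, and 0.372 (MBCT) and 0.338 (TAU) for (hypo)mania.

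The first quarter therefore dominates for depression. For (hypo)mania it is the largest quarter under this assumption but not dominant, and the medians themselves fall in months 3-6.

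**Size.** The protocol gives no rate for missing T1 and attending T2, so it is assumed and varied. The count outside SCID-I coverage = 80 x 12-month rate x miss rate x first-quarter share, taking missing T1 as unrelated to relapse. Ranges run from the 50% minimum to the exponential share.

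| Assumed miss rate | MBCT, per 80 | TAU, per 80 |
|---|---|---|
| 5% | 1.2-1.6 | 1.4-2.0 |
| 10% | 2.4-3.3 | 2.7-4.1 |
| 20% | 4.7-6.6 | 5.4-8.1 |

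For example, MBCT at 10%: 80 x 0.59 x 0.10 x 0.50 = 2.4, and with 0.697 it is 3.3. These are first depressive relapses before allowing for any that persist or recur and are caught at a later interview.

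**The case against.** Several points on the other side are good.

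- **The Life Chart.** Both arms keep it daily and it is planned for all 15 months, so a missed quarter is not necessarily lost to the trial. This stands as a partial safeguard. It is self-report, it may lapse in the patients who miss visits, and it has no assigned role in ascertaining relapse.
- **Later windows.** An episode that persists or recurs can be picked up at the next interview. This protects ever-relapsed status in part. It does less for time to first relapse and for episode counts.
- **Missing data.** Section 8 plans sensitivity analyses with imputed data, and no passage codes an unasked quarter as relapse-free. A reader might infer a spurious difference between arms. With 60% true risk in both arms and T1-missed/T2-attended rates of 10% v 20%, it would be 0.60 x 0.10 x 0.50 to 0.75 = 3.0 to 4.5 points; at 5% v 20%, 4.5 to 6.8 points. That requires coding as relapse-free, unequal attendance and no later detection. The documents state none of these, and T1 comes after the 8-week course has ended. Even 4 points is about half a standard error: sqrt(2 x 0.6 x 0.4 / 80) = 0.077.
- **The 40%.** Section 4.4 speaks of "taking account of a conservative estimate of 40% loss to follow-up". It is tempting to read this as the frequency of missed visits. It is not an intermittent-miss rate, and permanent dropouts gain nothing from a longer look-back.
- **Transfer from the earlier trial.** Section 1 describes that sample as euthymic at baseline, while this trial also admits currently depressed patients. The first-quarter share may differ here.
- **Unequal recall.** A look-back from the last interview gives some patients longer recall. That is a real cost, but longer recall taken by a blinded assessor is better than no SCID-I information for the quarter.

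**Conclusion.** The point holds as a weakness in how relapse is ascertained. Followed as written, sections 6.1.2 and 6.3 leave any skipped quarter outside SCID-I coverage even when the patient is interviewed next time, and shifted visits produce gaps or overlaps.

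The size is modest and conditional: about 2 to 4 first depressive relapses per arm of 80 at an assumed 10% miss rate, before later detection. It rests on the earlier trial's rates, on its medians being among relapsers, and at the upper end on exponential timing. The emphasis on months 0-3 belongs to depressive relapse and does not extend with the same force to (hypo)mania.

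The documents do not support saying that these relapses are lost to the trial altogether or that the comparison between arms is biased. Bias would depend on attendance differing by arm, which is not documented. The primary endpoint and the sample size are unaffected. The change is worth making because it is cheap and because later analysis cannot recover what was never asked.

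**What to change.** In section 6.1.2, state that each SCID-I covers depressive and (hypo)manic episodes since the last completed SCID-I, with onset month recorded so that each episode is counted once. Apply the same window to the T2-T4 telephone interviews in section 6.3. Add a sentence on whether and how the Life Chart is used when a SCID-I is missed.

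At the same time, reconcile T5: Table 1 lists the depression/mania SCID-I there, but the section 6.3 text for T5 omits it, and without it months 12-15 would have no SCID-I coverage.

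The cost is a few sentences and a change to the interviewer form, with no extra visit. The downside is a somewhat longer interview and longer recall for patients who missed a visit.

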#### Self-report measures

- *Quick Inventory of Depressive Symptomatology Self Report* (QIDS-SR; Rush et al., 2003). The QIDS-SR is a 16-item self-report version of the IDS-C. The QIDS-SR has good psychometric qualities.
- Altman self-rating mania scale (ASRM; Altman, Hedeker, Peterson, & Davis, 1997). The ASRM is a 5-item self-report questionnaire, with each item representing one of the major symptoms of mania, rated in increasing severity from 0 (not present) to 4 (present in severe degree). The ASRM has good psychometric properties.
- Prospective Life Chart, self-report, Dutch translation (Kupka, Akkerhuis, Nolen, & Honig, 1997). The Prospective Life Chart documents the course and severity of recurrent affective episodes. The current study will use the Life Chart prospectively in order to gain more fine-grained information about the severity of (hypo)manic or depressive symptoms over time, across the entire study period (15 months). The Life Chart has been shown a valid and reliable instrument to document the severity of affective episodes (Kupka et al., 1997).
- State/Trait Anxiety Inventory (STAI; Spielberger, 1983). The STAI is a self-report measure which has been proven reliable and sensitive in the assessment of both state and trait

levels of anxiety. It is a standard international measure in anxiety research and its Dutch translation has been shown valid (Van der Ploeg, 2000).

- Brooding subscale of the extended version of the Ruminative Response Scale (RRS-EXT; Treynor, Gonzalez, & Nolen-Hoeksema 2003). The authors reported adequate internal consistency (α = .79) and test–retest stability (α = .62, with a one year time interval) for the brooding subscale, which consists of five items. We select the brooding subscale because over time, brooding, or rumination, has been more strongly related to levels of depression (Treynor et al., 2003).
- The Comprehensive Inventory of Mindfulness Experience (CHIME; Bergomi, Tschacher, & Kupper, 2014). The CHIME is a 37-item, self-report questionnaire, divided in eight subscales measuring eight mindfulness aspects, including inner awareness, outer awareness, acting with awareness, acceptance, decentering, openness, relativity, and understanding. The CHIME has shown satisfactory to good change sensitivity, internal consistency, and test-retest reliability (Bergomi et al., 2014; Nila, Holt, Ditzen, & Aguilar-Raab, 2016).
- Self-Compassion Scale short form (SCS-SF; Raes, Pommier, Neff, & Van Gucht, 2011). The present study will use the 12-item Dutch short-form version of the SCS-SF to measure self-compassion. The scale consists of six components, including self-kindness, selfjudgment, common humanity, isolation, mindfulness and over-identification. The SCS-SF has good reliability and validity (Raes et al., 2011).
- Mental Health Continuum short form (MHC-SF; Lamers, Westerhof, Bohlmeijer, ten Klooster, & Keyes, 2011). Lamers, 2011). The MHC-SF is a 14-item self-report questionnaire that assesses emotional, psychological and social well-being. It has adequate psychometric qualities in terms of good internal consistency, (moderate) testretest reliability, and good divergent and convergent validity.
- Responses to Positive Affect- Dutch Version (RPA-NL; Feldman, Joormann, & Johnson, 2008). The RPA is a 17-item questionnaire measuring self-reported levels of dampening and rumination in response to positive affect. The RPA-NL shows a satisfactory internal consistency (Raes, Daems, Feldman, Johnson, & van Gucht, 2009).
- *Childhood Trauma Questionnaire* (CTQ; Bernstein et al., 2003). This questionnaire with 28 intems assesses five domains of abuse and traumatic experiences during childhood (physical abuse, emotional abuse, sexual abuse, physical neglect and emotional neglect). The CTQ shows good criterion-related validity (Bernstein et al., 2003).
- *Treatment Credibility Questionnaire* (TCQ; Borkovec and Nau, 1972, adapted version by Addis et al. (2004), with one additional item from the Credibility Expectancy Questionnaire (Devilly and Borkovec, 2000). The TCQ that will be used in this study consists of 7 items that focus on credibility and expectancy of treatment. The TCQ shows good reliability (Borkovec & Nau, 1972).

